8.3 TREATMENT REMOVAL

Patients will be removed from treatment in the event of:

- Peripheral neuropathy Grade >2 that does not improve as in Section 8.1
- Grade 3 or 4 hypersensitivity/infusion reaction.
- Inability of subject to comply with study requirements.
- Determination by the investigator that it is no longer safe for the subject to continue therapy.
- Progression of disease (as defined in Section 10.1).
- Delay of treatment \geq 2 weeks.
- Patient may choose to withdraw her participation at any time for any reason

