8.5 SERIOUS ADVERSE EVENT REPORTING

Where **adverse drug reaction** is defined as:

A noxious and unintended response to a medicinal product related to any dose. A causal relationship between the medicinal product and the adverse response is at least a reasonable possibility.

And **serious** is defined as:

A serious adverse event (experience) or reaction is any untoward medical occurrence that at any dose:

- Results in death
- Is life threatening

(Note: the term life-threatening in the definition of “serious” refers to an event in which the subject was at risk of death at the time of the event; it does not refer to an event which hypothetically might have caused death if it were more severe)

- Requires inpatient hospitalization or prolongation of existing hospitalization
- Results in persistent or significant disability/incapacity, or
- Is a congenital anomaly/birth defect

Medical and scientific judgment should be exercised in deciding whether expedited reporting is appropriate in other situations, such as important medical events that may not be immediately life-threatening or result in death or hospitalization but may jeopardize the subject or may require interventions to prevent one of the other outcomes listed in the definition above. These should also usually be considered serious.

All Serious Adverse Events (SAEs) will be reported to the IRB. Also, the Principal Investigator will report SAEs via the MedWatch Form 3500A to the FDA, which can be accessed at:

<http://www.accessdata.fda.gov/scripts/MedWatch/>

MedWatch forms will be sent to the FDA online at the above internet address or to the following:

MEDWATCH

[name]

[name]

FAX: [name] ([name])

The notification of a serious suspected adverse drug reaction should occur as soon as possible, but no later than one business day, and should be done by fax or email via the Eisai standard serious adverse event report form (attached hereto as Appendix B). The contact details for the notification are:

Eisai Medical Services
[name]
[name]
[contact]
[contact]
Email: [contact]

In addition, the Principal Investigator agrees to notify Eisai immediately of any other information that suggests a change to the safety profile of the Study Drug.

9.0

CLINICAL AND LABORATORY EVALUATIONS AND STUDY CALENDAR

Parameter	Pre-Treatment ⁵	Each Cycle ¹	Every 2 Cycles	Every 4 Cycles	Follow-Up (every 3 mos.) x 2 yrs	End of Study

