History & Physical Exam	X	X			X	
Weight, Performance Status	X	X				
Toxicity Assessment		X Day 1 and 8				
WBC (differential), Hgb, platelets	X	X Day 1 and 8				
Electrolytes, MG, BUN, Cr	X	X				
LFT (Bilirubin, AST, ALT, Alkaline phosphatase		X				
EKG	X			X		
CXR	X		X ⁶			
Radiology, x-ray or Scans for disease measurement	X		X			
Tissue collection ³	X					
Peripheral Blood Collection for Correlative Studies		X ⁴				X
Eribulin		Day 1 and 8				

¹ Within 24 hrs² As clinically indicated³ From paraffin embedded prior biopsy⁴ Cycles 1-6⁵ Within 28 days of each cycle⁶ CXR is only required in the event that a CT of the chest is not done. Should a CXR be given in place of a CT scan, an additional CXR should be repeated every 2 cycles.

10.0**CRITERIA FOR EVALUATION AND ENDPOINT DEFINITIONS**

The outcome status (in terms of toxicity, response, reason off study, progression, and survival) of all eligible patients will be reported. All eligible patients who begin treatment will be included in the analysis of response, survival and time-to-failure.

Toxicities and adverse events including laboratory adverse events will be graded and summarized according to the National Cancer Institute CTCAE, v4.3 (available on the NCI website at: <http://ctep.cancer.gov/forms/CTCAEv4.pdf>).

Response will be evaluated according to the RECIST criteria v1.1:

Eligibility

Only patients with measurable disease (at least one measurable lesion) at baseline should be included in protocols where objective tumor response is the primary endpoint.

Measurable lesions - lesions that can be accurately measured in at least one dimension with longest diameter ≥ 10 mm and 2x slice thickness on CT scan. Lymph nodes must be ≥ 15 mm in **short axis**. Bone lesions may be measurable if there is a lytic/soft tissue component that meets minimum size criteria. CXR lesions must be > 20 mm.

Non-measurable lesions - all other lesions, including small lesions or lesions not conventionally measurable (i.e. leptomeningeal disease, ascites, pleural/pericardial effusion, inflammatory breast disease, lymphangitis cutis/pulmonis, cystic lesions, and also abdominal masses that are not confirmed) should be noted and followed by imaging techniques but not measured.

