- Patients with a global deterioration of health status requiring discontinuation of treatment without objective evidence of disease progression at that time should be classified as having “symptomatic deterioration”. Every effort should be made to document the objective progression even after discontinuation of treatment.
- In some circumstances it may be difficult to distinguish residual disease from normal tissue. When the evaluation of complete response depends on this determination, it is recommended that the residual lesion be investigated (fine needle aspirate/biopsy) to confirm the complete response status.

Confirmation

- The main goal of confirmation of objective response is to avoid overestimating the response rate observed. In cases where confirmation of response is not feasible, it should be made clear when reporting the outcome of such studies that the responses are not confirmed.
- To be assigned a status of PR or CR, changes in tumor measurements must be confirmed by repeat assessments that should be performed no less than 4 weeks after the criteria for response are first met. Longer intervals as determined by the study protocol may also be appropriate.
- In the case of SD, follow-up measurements must have met the SD criteria at least once after study entry at a minimum interval (in general, not less than 6-8 weeks) that is defined in the study protocol

Duration of overall response

- The duration of overall response is measured from the time measurement criteria are met for CR or PR (whichever status is recorded first) until the first date that recurrence or PD is objectively documented, taking as reference for PD the smallest measurements recorded since the treatment started.

Duration of stable disease

- SD is measured from the start of the treatment until the criteria for disease progression are met, taking as reference the smallest measurements recorded since the treatment started.
- The clinical relevance of the duration of SD varies for different tumor types and grades. Therefore, it is highly recommended that the protocol specify the minimal time interval required between two measurements for determination of SD. This time interval should take into account the expected clinical benefit that such a status may bring to the population under study.

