10.1 ENDPOINT DEFINITIONS

10.1.1 PRIMARY EFFICACY ENDPOINT

Progression-free survival is defined as the time from first day of treatment to the first observation of disease progression or death due to any cause. If a patient has not progressed or died, progression-free survival is censored at the time of last follow-up.

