10.1.2 SECONDARY EFFICACY ENDPOINTS

The best overall response is the best response recorded from the start of the treatment until disease progression/recurrence (taking as reference for PD the smallest measurements recorded since the treatment started).

Overall survival is defined as the time from first day of treatment to time of death due to any cause. If a patient is still alive, survival time is censored at the time of last follow-up.

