13.0 STATISTICAL CONSIDERATIONS

Study Design: This is a two-stage, single arm study to obtain preliminary evidence of efficacy of Eribulin in the treatment of recurrent cervical cancer. Current chemotherapy treatments for recurrent cervical cancer are associated with response rates and 6-month progression-free survival rates no higher than 10%. The objective of this study is to determine whether there is evidence that treatment with Eribulin will result in response and 6-month PFS rates that exceed 10%, suggesting promising activity and encouraging further study.

The primary efficacy endpoint will be 6-month progression-free survival (PFS₆). The secondary efficacy endpoint will be best overall response (BOR). A total of 30 patients who are fully evaluable for PFS₆ will be enrolled on this study. Patients who are not fully evaluable for PFS₆ will be replaced. Replaced patients will nonetheless be included in the final efficacy analysis. PFS₆ will be the endpoint for interim monitoring.

An interim analysis will occur when 15 patients have been evaluated for PFS₆, with final analysis once 30 patients have been evaluated for PFS₆. $\geq 1/15$ patients who achieve PFS₆ are required to continue study accrual to 30 patients. $\geq 6/30$ patients who achieve PFS₆ will be considered sufficient evidence of efficacy to warrant further study. The study will be terminated if fewer than 1/15 patients are progression-free at 6 months. The study may remain open pending the interim results on the first 15 patients, but will be suspended to enrollment if the 20th patient is enrolled before the interim results are available.

Sample size justification. This design has one-sided Type I error of <0.10 (0.072) for a true PFS₆ rate of 10%, and power of at least 0.80 for a true PFS₆ rate of 26%. Hence this study has sufficient power to detect moderate and clinical important improvements in PFS₆ rate due to Eribulin treatment when compared to past experience with chemotherapy treatment of recurrent cervical cancer.

Additional efficacy analyses. Product limits estimates of 6-month PFS will be computed using all patients enrolled on the study. 95% confidence intervals will be based on Greenwood standard errors. In addition, exact 95% binomial confidence intervals will be compute for the BOR rate.

Toxicity analyses. The rate of Grade 3+ hematology and non-hematologic toxicities will be computed for course 1 and for all courses combined.

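### PFS is censored at last follow-up rather than at the last tumour assessment, so unscanned time can count as progression-free in the 6-month PFS

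*Combined protocol and SAP*

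**What the plan says.** Section 10.1.1 defines PFS from the first day of treatment to first observed progression or death, and adds: "If a patient has not progressed or died, progression-free survival is censored at the time of last follow-up". Section 10.1.2 has the parallel sentence for overall survival: "If a patient is still alive, survival time is censored at the time of last follow-up".

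The section 9.0 calendar has a row "Radiology, x-ray or Scans for disease measurement". As extracted, it is marked at pre-treatment and every 2 cycles. The column "Follow-Up (every 3 mos.) x 2 yrs" is marked only for history and physical examination. Footnote 2 of the calendar, which refers to clinical indication, has no visible anchor in the extracted text.

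Section 8.3 lists ways of leaving treatment without progression, among them "Determination by the investigator that it is no longer safe for the subject to continue therapy", non-compliance, treatment delay and withdrawal. Section 10.0, on symptomatic deterioration, says: "Every effort should be made to document the objective progression even after discontinuation of treatment".

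Section 13.0 makes 6-month PFS (PFS6) the primary efficacy endpoint. At least 1 success in 15 continues accrual, and at least 6 in 30 supports further study. Patients not fully evaluable for PFS6 are replaced, and that term is not defined. The section adds: "Replaced patients will nonetheless be included in the final efficacy analysis". Product-limit estimates of 6-month PFS use all enrolled patients. Section 10.0 says: "All eligible patients who begin treatment will be included in the analysis of response, survival and time-to-failure".

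**The concern.** Vital status is known at any contact. Progression status is not, when it rests on RECIST 1.1 measurement. A rule that suits overall survival therefore credits PFS with time during which nobody may have looked for progression.

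The affected patient stops treatment without progression, attends a follow-up visit after month 6, and has had no scan since she stopped. Under section 10.1.1 she is progression-free up to that visit. She stays in the product-limit risk set past 6 months, and nothing in section 13.0 prevents her being counted as a PFS6 success. The section names no assessment that must support that status.

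The decisions rest on small counts in a single-arm, open-label trial. One such patient in the first 15 satisfies the interim rule alone, and one among 30 is a sixth of the number needed at the end.

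**Working it through.** **Inputs from the plan (section 13.0):** 15 patients then 30; continue if at least 1/15; success if at least 6/30; null rate 10%, alternative 26%; stated one-sided type I error 0.072 (limit 0.10) and power at least 0.80. Cycles are 21 days (section 3.0), so scans every 2 cycles fall nominally at weeks 6, 12, 18, 24 and 30.

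**Assumed inputs:** every count of unscanned or replaced patients below. The documents give none.

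**1. The plan's own figures.** With X1 and X2 the successes in each group of 15,

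P(pass) = Σ over x = 1 to 15 of P(X1 = x) × P(X2 ≥ 6 − x), both Binomial(15, p).

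- p = 0.10: 0.0727, which agrees with the stated 0.072 apart from rounding.
- p = 0.26: 0.828, consistent with at least 0.80.
- Interim stopping probability at p = 0.10: 0.9^15 = 0.206.

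**2. Unscanned patients wrongly counted as successes.** Treat k of the 30 as credited successes and the others as having a true 10% rate. For k = 1 in stage 1 the interim rule is already met, so P(pass) = P(Binomial(29, 0.10) ≥ 5).

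| Wrongly credited | P(pass) at a true 10% rate |
|---|---|
| 0 | 0.073 |
| 1 | 0.157 (in stage 2) to 0.158 (in stage 1) |
| 2 | 0.298 to 0.305, by stage |

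**3. Product-limit estimate, invented example.** Take 30 patients with 18 events by week 12, leaving 12. Ten of these are scanned on schedule, and 3 of the ten are event-free at 6 months. The other two have a last clear scan at week 12 and an unscanned visit after month 6.

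- Censoring at last follow-up: (3 + 2)/30 = 16.7%.
- Censoring at last clear scan: (12/30) × (3/10) = 12.0%.

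The Greenwood standard error of the first figure is √(0.167 × 0.833/30) = 0.068, giving a 95% interval of about 3% to 30%. The shift lies well inside the sampling error, but it goes in one direction.

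**4. Replacement.** Suppose a share r of patients is replaced, all of them failures, with a true rate of 10% overall. The rate among the 30 retained is then 0.10/(1 − r).

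| r | Retained rate | Replaced patients left out; bar 6/30 | Replaced patients counted; 20% bar on everyone |
|---|---|---|---|
| 10% | 0.111 | 0.108 | 0.043 (7 of about 33) |
| 20% | 0.125 | 0.163 | 0.027 (8 of about 37 or 38) |

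The last column applies the two-stage formula with the final bar raised to 7 or 8, because 0.20 × 33.3 = 6.7 and 0.20 × 37.5 = 7.5. The 20% bar is 6/30 carried over to the larger denominator; the plan does not state it. If replaced patients do as well as the others, the first reading stays at 0.073.

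**The case against.** **Progression is not found by scan alone.** Section 10.1.1 speaks of observing progression, section 10.0 accepts superficial lesions assessed clinically, and the treating physician's opinion carries weight for non-target lesions. A patient who is well at a month-6 examination may truly be progression-free, and counting her then inflates nothing. This stands. The figures 0.16 and 0.30 are conditional on misclassification having occurred, and a reader should not take them as the design's type I error.

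**The calendar may be incomplete.** Footnote 2 has lost its anchor, and the liver function row shows no pre-treatment mark although eligibility depends on those tests. A mark for off-treatment scans could also have been lost, so the original should be checked. Even if footnote 2 belongs to the follow-up column, scanning on clinical indication would not guarantee an assessment near month 6.

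**Censoring formally enters only the product-limit estimate.** That analysis is additional, and the decision rules count patients evaluated for PFS6. This is correct, but section 13.0 gives no separate definition of PFS6 status, so the reader falls back on section 10.1.1. The request in section 10.0 to document progression concerns symptomatic deterioration; it sets no date and does not say how an unscanned patient is scored.

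**Replaced patients remain in the final efficacy analysis.** A reader might infer from the replacement rule that the success rate is inflated. The documents do not support that. Section 13.0 says these patients are included, and under one reading the error rate falls rather than rises. What is missing is a statement of how they enter the counts.

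**Conclusion.** The censoring point holds. Section 10.1.1 applies a survival rule to an endpoint that depends mainly on lesion measurement. Followed as written, it credits unscanned time as progression-free in the product-limit 6-month PFS and allows an unscanned patient to be read as a PFS6 success. This rests on the calendar as extracted, subject to checking the original.

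The size depends on assumed counts. One false success among 30 moves the chance of passing at a true 10% rate from 0.073 to about 0.16, above the plan's 0.10 limit; two move it to about 0.30. How often this would happen cannot be judged from the documents.

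The replacement point is a request for clarification only. Depending on the reading, the error rate could exceed 0.10 or fall to about 0.03 to 0.04.

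Two stronger readings are not supported. The sample-size calculation is not wrong, since its figures reproduce. Nor does it follow that every patient without a week-24 scan must be scored a failure. If 10% of true successes lacked such a scan, p = 0.26 × 0.90 = 0.234 and power falls to 0.734. At 20%, p = 0.208 and power is 0.61. The 10% benchmark comes from literature whose assessment schedule the documents do not give, so that rule could be stricter than the benchmark.

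**What to change.** 1. In section 10.1.1, censor PFS at the last tumour assessment showing no progression. Leave the overall survival rule in section 10.1.2 unchanged.
2. In section 13.0, require each PFS6 success to be supported by a tumour assessment rather than contact alone, using existing scans. State in advance which assessment qualifies. Six months is about week 26, between the nominal week-24 and week-30 scans, so a patient last scanned at week 24 could count as a success in the rule yet be censored earlier in the product-limit estimate. The text should cover that case.
3. In section 13.0, state how replaced patients enter the 1/15 and 6/30 counts. One option is to report PFS6 in all eligible treated patients, as section 10.0 implies, alongside the rule.
4. Offer the scoring of all patients without a week-24 scan as failures only as a sensitivity analysis.

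**Cost:** wording in two sections, with no scan added or moved. Observed PFS6 may be slightly lower. Some patients will be censored earlier, which removes information from the product-limit estimate and could itself bias it if those who stop early differ from the rest.

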10.1.2 SECONDARY EFFICACY ENDPOINTS

The best overall response is the best response recorded from the start of the treatment until disease progression/recurrence (taking as reference for PD the smallest measurements recorded since the treatment started).

Overall survival is defined as the time from first day of treatment to time of death due to any cause. If a patient is still alive, survival time is censored at the time of last follow-up.

10.1.3 PRIMARY TOXICITY ENDPOINTS

The primary toxicity endpoint is any occurrence of grade 3+ hematologic and non-hematologic toxicity according to CTCAE4.3.

11.0 SPECIAL INSTRUCTIONS

To determine the association between responsiveness to eribulin and prognostic factors such as apoptosis markers, proliferation, pAkt, EGFR, and ER stress, we propose examination of primary tumor specimens using immunohistochemistry. At the time of enrollment, the original cervical tumor tissue and corresponding H&E slide from all patients will be retrieved from the pathology archive. Because of the nature of the patient population at this institution, the primary diagnosis of cervical cancer is typically made within this same institution. If sufficient tissue is remaining within the paraffin block, 20 additional unstained sections will be obtained from these paraffin blocks for immunohistochemistry. Blocks will be retrieved by the USC-Norris Translational Pathology Core under the direction of [name] [name] and the lab manager, [name]. These immunohistochemistry experiments will be performed in [name] laboratory in the Harlyne Norris Research Tower at the USC Norris Comprehensive Cancer Center. Scoring will be performed by a board-certified gynecologic pathologist.

In patients who undergo a biopsy or surgical procedure to demonstrate recurrent cervical cancer, the archived paraffin block will be retrieved in addition to the original tumor block, and 20 unstained sections will be obtained from the paraffin block for immunohistochemical comparison of the paired primary and recurrent tumor. The priority of immunohistochemical studies are as follows: 1) expression levels of microtubule-associated variables, including τ protein, total α - and β -tubulin, and classes II-IV β -tubulin isotopes, 2) pAkt/EGFR, 3) UPR markers (CHOP, GRP78, eIF2 α), 4) p53, 5) TUNEL, Bcl-2, Bax, 6) Ki67.

For the serum studies measuring GRP78, we plan to utilize an ELISA-based tool. Serum specimens will be obtained prior to the infusion of each eribulin as described in the protocol. We will plan to obtain a maximum of 7 serial serum samples (cycles 1-6, end of study drug) in order to permit interval radiographic assessment of tumor volume as dictated in the primary treatment protocol. Serum will be collected into a separate (standard 6mL) Vacutainer at the time of standard pre-chemotherapy labs (plain red-top tube containing no anticoagulants or preservatives). Since all chemotherapy patients on protocol are seen in clinic on a designated day each week, the blood will be collected and transported to [name] lab for processing (i.e., centrifugation, pipette-transfer into tube for -80°C storage prior to batching for assay and analysis). Specimen procurement will be performed by the USC-Norris Translational Pathology Core. The tumor volume will be ascertained by the study radiologist in accordance with the primary protocol.

12.0 DATA COLLECTION AND MONITORING

12.1. CONFIDENTIALITY OF RECORDS

The original data collection forms will be kept in secure file cabinets in the CISO.

12.2. PATIENT CONSENT FORM

At the time of registration, three signed and dated copies of the patient Informed Consent form with the Human Rights and the HIPAA authorization must be available (for patient, patient's medical chart and one for the Clinical Investigations Support Office).

